METHODS: Participants will undergo a series of three assessments within a one week time frame prior to initiating intervention. Intervention using the TPAD and overground training will occur the following week for five consecutive visits. On completion of the final training visit, participants will be re-assessed, and return for a single follow up visit the next week for the final assessment. Each study visit will be approximately 1-1.5 hours in duration, and total participation should be completed within three weeks.

EXPECTED OUTCOMES: We anticipate this training paradigm will prove feasible in reducing both load and stance asymmetry in a population of individuals with chronic stroke.

II. Research Questions:

- 1) Is a five day gait training program using the TPAD and incorporating augmented visual feedback and an overground walking component feasible in terms of safety, treatment tolerance, and adherence in individuals with chronic stroke who present with gait asymmetry?
- 2) Is this training program effective at improving load force symmetry after five sessions?
- 3) Is this training program effective at improving stance time symmetry in overground gait?

III. Study Design/Methodology

This is a single arm, non-randomized pilot study of feasibility. The study population and details of study procedures are specified below.

IV. Outcome Measures

A. Primary Outcomes

- Measures of Feasibility
 - Safety
 - Adverse Events / Serious Adverse Events
 - Adherence
 - Attendance Rates of Study Visits
 - Tolerance
 - Ratings of Perceived Exertion (RPE)
 - Heart Rate (HR)
- Efficacy
 - Overall Load Force Symmetry (over the course of training)
 - Stance Time Symmetry

B. Secondary Outcomes

- Daily Load Force Symmetry (intraday changes in load force)
- Time in Double Support
- Swing Time Symmetry
- Stride Length Symmetry
- Stride Velocity Symmetry
- Gait Velocity
- Balance (as per the Berg Balance Scale)

V. Study Population

A total of 12 adults (ages 18-75) will be recruited for participation from a voluntary stroke registry, anticipating 20% attrition, or that at least 10 participants will meet criteria and complete study participation.

Inclusion Criteria:

- Chronic (>6 months) stages post stroke
- History of a single stroke event (either ischemic or hemorrhagic by origin)
- Minimal score of 22 or higher on the MoCA
- Must be independent community ambulator (with/without AFO)
- May use a unilateral assistive device (cane, quad cane)

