During this time vertical forces (F_z) will be taken for each the paretic and non paretic limb.

- t.** Video recordings will be made from a posterior view during minutes 5 of post training.
- u.** On completion of post training, participants will be assisted off of the treadmill and reflective markers, safety harness, pelvic belt and arm sling will be removed.
- v.** HR and RPE will be taken and recorded on CRF_TPAD_Form_02 (See attached).

3. Overground Training

- a. Participants will then initiate overground training for which they will ambulate in a quiet corridor and will receive verbal and gentle tactile cues to reinforce TPAD training. Overground training will be between 5-10 minutes. Duration of overground training period will be recorded.
 - Verbal cues will include:
 - “Remember to walk and put as much weight on your right/left (paretic) limb as possible and keep it there as long as possible.”
 - “Can you put more weight on your right/left (paretic) side?”
 - “A little more”
 - “More weight over here”
 - “Keep it/your weight there a little longer with each step.”
 - Tactile cues will include:
 - Gentle tapping at right/left (paretic) side.
 - Gentle tapping at right/left (paretic) quadriceps.
 - Light hand hold around pelvis with gentle weight shift onto paretic side.
- b. On completion of overground training, HR and RPE will be taken and recorded one additional time on CRF_TPAD_Form_02 (See attached).
- c. CRF_TPAD_Form_02 will be completed daily for each intervention session.
- d. Any incidents with patient safety during interventional procedures will be reported on CRF_TPAD_Form_02.
- e. Any missing visits** occurring during intervention will also be noted on CRF_TPAD_Form_02.
- f. This will conclude the training portion of the session.

VII. Participant Withdrawal

Participation in this study is voluntary. Participants will be allowed to withdraw from the study at any point. Withdrawal of participation from this study will not preclude individuals from participating in any future studies relating to stroke or for which the individual would be a potential candidate.

The participant may be withdrawn by a member of the research team if:

- The participant does not complete all Pre-Test Assessments.
- The participant completes < 4/5 training visits
- The participant does not complete Post-Test Assessment
- The participant sustains an injury while participating that would prevent s/he from completing study procedures

VIII. Risk / Benefit

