No invasive interventional procedures will be used during these study procedures. Thus, this is a low risk study. General risks of exercise are expected during study participation, including but not limited to muscle fatigue, muscle stiffness, and muscle soreness. In an effort to minimize risk to participants, a licensed physical therapist will be present for all study related activities. Additionally, a MD will be available in the event of an injury or the occurrence of an adverse event. Any medical injuries sustained during participation in this study will be recorded (CRF_TPAD_Form_02), and the Principle Investigator and the Institutional Review Board will be notified within 24 hours of event. The study participant will be responsible for any incurred cost from a study related injury.

We anticipate that participants who complete study procedures may receive improvement in gait symmetry by participating in this trial. However, we cannot guarantee physical benefit from study participation. Additionally, it is likely that any benefit in gait performance seen from participating in this trial will be temporary and not long-lasting due to the short duration (one week) of the intervention.

IX. Data Management/ Storage

Hard copies of CRF and study documents will be stored in files coded by patient identification numbers assigned at the onset of study participation. These files will be stored in a locked file cabinet in the office of a member of the study team. Only team members will have access to these files.

Electronic data will also be coded using the same patient identification numbers. A code key will be located in the hard copy files. All electronic data will be stored either in a REDCap Database (feasibility results of safety, adherence, treatment tolerance, gait velocity and balance scores) or on a CUMC encrypted end point device (gait data from embedded force plates and APDM inertial sensors) that is backed up regularly. Patient data sheets will be input into the REDCap database and each member of the study team will have access via an individualized login/password combination. Coded copies of electronic data will be shared between members of the research team via Columbia University email

system. To ensure data security, all electronic data will be coded, and the code key will not be included with data files.

X. Adverse Event Reporting

Adverse events include study related injuries including, but not limited to:

- Falls
- Ankle sprains/strains

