- Fractures
- Orthopedic related injuries
- Dizziness
- Severe fatigue that requires a ceasing of study procedures

In the case of an adverse event (AE), the participant will be evaluated immediately by the physical therapist present for all study procedures. If the AE persists, study procedures will be stopped, and the study MD notified to evaluate the participant. In such cases where applicable (e.g. fracture, ankle injury) the participant will be referred and assisted to the Emergency Room for immediate attention.

All AEs will be recorded and reported to the PI and IRB within 24 hours.

XI. Statistical Analysis

Please see attached Statistical Analysis Plan.

XII. Dissemination of Results and Publications

Results of this work will be analyzed and a manuscript prepared for publication. Full details of this work including prior work using the TPAD, background, study procedures, statistical analysis procedures and detailed results will be written and stored on file as a part of the final dissertation report.

[name], PT, DPT will serve as primary author on the dissertation with [name], EdD providing sponsorship. [name] will also serve as a primary author for manuscripts prepared discussing the feasibility and preliminary efficacy of the TPAD to reduce asymmetry in a population of individuals after stroke. [name], MS will serve as primary author for any manuscripts detailing technical specifics of implementing TPAD treatment in a population of individuals after stroke. Other participating members of the research team will be recognized in authorship in all manuscripts submitted for publication.

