### **Study Outcomes**

#### **1. Feasibility**

The primary feasibility outcomes will include an evaluation of safety, tolerance to treatment, and adherence over the course of the trial.

**1.1.** Safety of the intervention will be assessed by recording the number of adverse events (AE) and/or serious adverse events (SAE) that occur throughout the duration of the trial and will be reported as summary data.

**1.2** Treatment tolerance will be measured primarily by rates of perceived exertion (RPE) and secondarily by the percentage of maximum heart rate (HRmax) throughout daily training sessions.

**1.3** Rates of adherence will be presented as a proportion of visits attended out of the total study visits. Participants who are not able to complete at minimum four out of the five training visits (80% adherence) will not be included in the final data analysis.

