## **4.1 Feasibility Measures**

### **4.1.1 Safety**

#### **Assessed at each study visit**

All falls, injuries, and any safety concerns that arise will be recorded on paper forms and reported summarily.

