## **2. Analysis of Primary Outcomes**

### **2.1 Primary Outcomes of Feasibility**

#### ***2.1.1 Safety***

All adverse events (related to participation) including any injuries or falls will be reported summararily in the final report.

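### SAP 2.1.1 qualifies the reported adverse events as related to participation and omits SAEs, which conflicts with the primary safety outcome of all AEs and SAEs

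*SAP*

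**What the plan says.** Safety is the first element of the primary feasibility question in both documents, and several places describe what will be counted.

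- **Protocol IV.A, Primary Outcomes:** the safety measure is listed as "Adverse Events / Serious Adverse Events", without a qualifier.
- **SAP, Study Outcomes, 1.1:** safety will be assessed by "recording the number of adverse events (AE) and/or serious adverse events (SAE) that occur throughout the duration of the trial", presented as summary data.
- **SAP 4.1.1, Safety (assessed at each study visit):** "All falls, injuries, and any safety concerns that arise will be recorded on paper forms and reported summarily".
- **SAP, Statistical Analyses, 2.1.1, Safety:** "All adverse events (related to participation) including any injuries or falls will be reported" in summary form in the final report. Serious adverse events are not named.
- **Protocol X, Adverse Event Reporting:** "Adverse events include study related injuries including, but not limited to", followed by a list running from falls to severe fatigue. The section ends: "All AEs will be recorded and reported to the PI and IRB within 24 hours".

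The available text of the two documents gives no criteria for deciding whether an event is related to participation, names no role to decide it, and plans no separate listing of unrelated events.

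**The concern.** The outcome as defined and the outcome as analysed are not the same. SAP 1.1 and 4.1.1 call for everything that happens. SAP 2.1.1, which governs the final report, attaches a relatedness condition in parentheses. Neither document says which wording prevails.

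An analyst who follows 2.1.1 literally could leave out an event considered unrelated. In a single-arm study there is no control rate to help decide whether, say, a fall in a chronic stroke survivor owes anything to the training. With no stated criteria, the decision would rest on whoever makes it at the time.

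The SAP describes the feasibility measures as critical for planning later randomised trials. A safety count that depends on an unspecified attribution step is a weaker basis for that planning, and any error would make the intervention look safer.

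**Working it through.** **Step 1. Compare the definitions.**

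| Place | Relatedness condition | SAEs named | What is promised |
|---|---|---|---|
| Protocol IV.A | None | Yes | Listed as primary outcome |
| SAP 1.1 | None | Yes | Recorded, summary data |
| SAP 4.1.1 | None | No | Recorded and reported |
| SAP 2.1.1 | Related to participation | No | Reported in the final report |
| Protocol X | Leans to study-related injuries, open-ended | No | Recorded, sent to PI and IRB |

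Only the analysis section attaches an explicit relatedness condition to what is reported.

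**Step 2. Direction.** Let A be the number of all adverse events, U the number considered unrelated, and R the number reported under the condition. Then R = A − U with U ≥ 0, so R ≤ A. The condition can leave the count unchanged or lower it. It cannot raise it.

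**Step 3. Size, for illustration only.** The documents give no expected adverse event rate, no safety threshold and no planned safety interval, so there is no stated figure to reproduce. The inputs are 12 participants enrolled (SAP, Figure 1 text) and 10 expected to complete (protocol, Participants). The number of participants with an event is my assumption.

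Exact (Clopper-Pearson) two-sided 95% limits for x participants out of n:

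- lower = Beta quantile at 0.025 with parameters (x, n − x + 1), and 0 when x = 0
- upper = Beta quantile at 0.975 with parameters (x + 1, n − x)

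For x = 0 the upper limit reduces to 1 − 0.025^(1/n). With n = 12 this is 1 − 0.025^(1/12) = 0.265.

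| Participants with an event | All events reported | Reported if all of these are dropped |
|---|---|---|
| 1 of 12 | 8.3% (0.2% to 38.5%) | 0% (upper limit 26.5%) |
| 2 of 12 | 16.7% (2.1% to 48.4%) | 0% (upper limit 26.5%) |
| 3 of 12 | 25.0% (5.5% to 57.2%) | 0% (upper limit 26.5%) |
| 1 of 10 | 10.0% (0.3% to 44.5%) | 0% (upper limit 30.8%) |

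All limits are two-sided so that the columns can be compared. The one-sided 95% upper bounds for 0/12 and 1/12 are 22.1% and 33.9%. They should not be mixed with the two-sided figures.

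One attribution decision moves the two-sided upper limit at n = 12 by 38.5 − 26.5 = 12.0 percentage points, and changes the headline from one participant affected to none.

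**The case against.** The strongest reply is that 2.1.1 does not say that only related events will be reported, and that SAP 4.1.1 separately promises summary reporting of all falls, injuries and safety concerns. An unrelated fall could still reach the report by that route. The parenthesis may also be a loose echo of protocol X. This stands to the extent that exclusion of unrelated events is not certain. It does not remove the conflict, because 4.1.1 and 2.1.1 then give different instructions for the same report.

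A second reply is that the SAP plans no safety proportion, interval or go/no-go rule, and that SAP 1.1 counts events and not participants. That also stands. No planned statistic or decision is shown to change, and the figures above only give scale.

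A reader might infer three stronger things that the documents do not support:

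- **That the protocol restricts adverse events to study-related injuries.** Section X uses open-ended wording, so it leans that way without excluding other events.
- **That unblinded staff will judge relatedness.** No relatedness assessment is described at all. The gap is the missing procedure, not a known flawed one.
- **That events between visits will go unrecorded.** One instruction is tied to sessions: "Any incidents with patient safety during interventional procedures will be reported on CRF_TPAD_Form_02". But protocol VIII requires medical injuries sustained during participation to be recorded, protocol X covers all AEs, and SAP 4.1.1 applies at each visit. The case report forms are not in the available text and may already ask about events since the last visit.

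**Conclusion.** The point holds as an inconsistency in a primary outcome. SAP 2.1.1 carries a relatedness condition and omits SAEs, in conflict with SAP 1.1, SAP 4.1.1 and the protocol's outcome list. If 2.1.1 is applied literally, the reported safety result could understate events and cannot overstate them.

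The size cannot be derived from the documents. On the assumption that one of 12 participants has an event and it is dropped, the result moves from 8.3% to 0%, with the limits shown above. Whether anything would be dropped depends on which section the analyst follows and on attribution decisions for which no rules are given.

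This should be corrected before analysis. It does not show that the safety result will be wrong, and it does not show that event recording is deficient.

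**What to change.** Reword SAP 2.1.1 so that it matches SAP 1.1. The final report would give all adverse events and all serious adverse events from consent to Follow Up, as the number of events and the number of participants with at least one. Show relatedness to participation as a separate column and not as a condition for inclusion. State briefly the criteria for relatedness and the role that assigns it.

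Align the opening of protocol Section X with this, so that adverse events are not introduced mainly as study-related injuries.

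Optionally, ask at each visit about events since the last one and record the answer on the existing forms. Check the forms first, because the question may already be there.

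The cost is wording in two places and one extra table column. The report may show a slightly higher event count. Sample size, visits and treatment do not change.

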#### ***2.1.2 Treatment Tolerance***

Group means (SD) of Rate of Perceived Exertion (RPE) over the course of the intervention will be reported summararily for the group. A repeated measures analysis of variance (ANOVA) will be used to determine effect, or change of RPE over the course of the intervention (by day). The percentage of maximum heart rate (HRmax) will also be reported using descriptive measures (mean, standard deviation) for the group, and a repeated measures ANOVA used to assess for change over the course of the intervention.

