Prior to initiating the training, a member of the research team will complete the Treatment Checklist, including:

[figure not shown]
- a. Participants will stand while reflective markers are placed bilaterally at:
 - ✓ R/L Medial & Lateral metatarsal heads
 - ✓ Superior surface of first distal toe
 - ✓ R/L Med & Lateral malleoli
 - ✓ R/L Heel
 - ✓ R/L Tibial Plateau
 - ✓ R/L Fibula Head
 - ✓ R/L Med & Lateral distal Femur
 - ✓ R/L anterior shaft of the Femur (at midpoint)
 - ✓ R/L lateral shaft of the Femur (at midpoint)
 - ✓ Anterior Superior Iliac Spine (ASIS)
 - ✓ Superior (on abdomen) to ASIS for ASIS Recreation
 - ✓ L3

- b.** Patient clothing will be taped in place to ensure marker visibility throughout treatment.
- c.** Participants will then don:
 - ✓ A safety harness that will connect to an overhead metal brace/beam during gait tasks on the treadmill.
 - ✓ A sling to support the paretic arm during gait. This is done to prevent the blocking of reflective markers during gait that are needed for the application of forces.
 - ✓ A pelvic belt that has been altered to allow the attachment of force tethers.
- d.** Heart Rate (HR) monitor and Borg Scale will be in place to allow recordings throughout treatment session.

- e. Participants will then be assisted onto the dual belt treadmill.
- f. A still image will be recorded using a Vicon® infrared recording system and evaluated to ensure all markers are in place and are visible.
- g. During the still image, recordings will be made of vertical forces (Fz) during quiet stance for both the paretic and non-paretic limb.
- h. Measures of resting heart rate (HR) and Ratings of Perceived Exertion (RPE) will be taken and recorded on CRF_TPAD_Form_02 (See attached).

2. Treadmill Training

- a. The treadmill will be initiated and speed gradually increased by 0.1 m/s intervals. The participant will be asked when s/he feels this will be a challenging, yet tolerable speed to sustain for one hour (60 minutes). A supervising Physical Therapist will confirm the speed and this will be recorded on CRF_TPAD_Form_02 (See attached). The confirmed speed will be used for all subsequent treatment sessions. *This will occur during Day 1 treatment ONLY.
- b. The participant will continue walking at the self-selected gait speed for five minutes.

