Following these three visits of Pre-Test assessments, participants will return to complete five consecutive days of the training intervention. The intervention will consist of five consecutive days of TPAD training plus visual feedback training with a short over ground training (5-10 minutes) each day immediately following completion of treadmill based activities. After participants are readied for intervention, they will be assisted onto the treadmill and the treadmill will be initiated. Individuals will self-select gait speed with a physical therapist confirming speed is safe for the duration of training. Once gait speed is set, individuals will initiate five minutes of Baseline gait on the treadmill during which load force measures are recorded at minute 0-1 (BL1), minute 2-3 (BL2) and minute 4-5 (BL3). This Baseline gait will be followed by 40 minutes of tethered TPAD training with visual feedback provided. The amount visual feedback will be faded over the course of the five-day training. On completion of the tethered portion of training, participants will continue to ambulate on the treadmill for an additional 10 minutes during a Post-Training period. Measures of load force will be recorded during minute 0-1 (PT1), minute 3-4 (PT2), minute 6-7 (PT3) and minute 9-10 (PT4) of Post Training. Participants will then be assisted off the treadmill and an additional 5-10 minutes of over ground training will be conducted reinforcing weight shifting onto the paretic limb. Participants will be required to complete at least four days of training for data to be considered in the final analysis. Training sessions will last approximately 60 minutes (one hour) in duration.

On the fifth day of training, immediately following the final training session, participants will be allowed a 10-15 min seated rest break and over ground measures will be reassessed (Post

Test). All participants will be asked to return one week after completion of the intervention to undergo one final over ground assessment (Follow Up).

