## **Statistical Analyses**

Statistical assumptions and normality will be tested prior to running statistical analysis for measures of treatment tolerance, force symmetry, spatiotemporal gait parameters including stance symmetry and balance. A *p value* of 0.05 or lower will be considered statistically significant for all analyses.

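### The only test of change in exertion (SAP 2.1.2) ignores day order and direction and comes with no interval; adding a Day 1 to Day 5 slope with a 95% CI would be a cheap improvement

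*SAP*

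**What the plan says.** The Protocol (IV.A) lists RPE and heart rate as the tolerance measures among the primary outcomes. The SAP ranks them (Study Outcomes, 1.2): "Treatment tolerance will be measured primarily by rates of perceived exertion (RPE) and secondarily by the percentage of maximum heart rate (HRmax"). SAP, Specific Objectives, counts tolerance among the measures that will answer the feasibility question.

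SAP 2.1.2 plans two things for each measure. The first is descriptive: for RPE, group means (SD) "over the course of the intervention will be reported summararily for the group". The second is a test. For RPE, a repeated measures ANOVA "will be used to determine effect, or change of RPE over the course of the intervention (by day"). For %HRmax, "a repeated measures ANOVA used to assess for change over the course of the intervention"; here the by-day structure is not repeated. The general rule is that a p value "of 0.05 or lower will be considered statistically significant for all analyses".

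SAP 2.1.2 names no contrast, direction, effect size, interval or tolerance criterion. By comparison, SAP 2.2.1, 2.2.2 and 3.1 to 3.8 all ask for effect sizes and 95% confidence intervals. SAP 2.2.2 also plans regressions over time for stance symmetry, with the slope reported, to judge change across the intervention. Safety (2.1.1) and adherence (2.1.3) are reported descriptively.

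**The concern.** The training covers "five consecutive days of the training intervention", and treadmill speed is set on Day 1: "The confirmed speed will be used for all subsequent treatment sessions" (Protocol VI.D.2, step a). Tether force and the 40-minute tethered period are also the same each day. The natural question is therefore whether exertion drifts up or down across the week, and by how much.

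A by-day F test asks something else: whether any of the five day means differ. Shuffling the days, or turning a rise into an equal fall, leaves F unchanged. Its 4 numerator degrees of freedom spread power over patterns that are not of main interest. For tolerance, no change is a reassuring result, and about 10 people will contribute. Without an interval, a reader of a non-significant result cannot tell a flat course from a rise too imprecisely measured to detect.

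**Working it through.** **Inputs from the documents.** Two-sided alpha 0.05 (SAP, Statistical Analyses); five training days; 12 recruited to give at least 10 completers at 20% attrition (Protocol V). The stated figure checks: 12 × 0.8 = 9.6, about 10. No power is stated for any test.

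**Assumptions, none in the documents.** SD of one daily value = 1; compound-symmetric between-day correlation ρ of 0.5 to 0.8; a linear rise of 0.5 SD from Day 1 to Day 5; no missing days. For %HRmax, 4 df is also inferred.

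**Omnibus F.** Day means are 0, 0.125, 0.25, 0.375 and 0.5, with mean 0.25. The sum of squared deviations is 2(0.25²) + 2(0.125²) = 0.15625. The noncentrality is λ = n × 0.15625/(1−ρ), with df 4 and 4(n−1) = 36 at n = 10. The critical F is 2.63.

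**Linear slope.** The fitted Day 1 to Day 5 change is 4 × slope. The centred days have sum of squares 10, so SE = √(16(1−ρ)/(10n)) = √(1.6(1−ρ)/10) at n = 10. The test is a t on n−1 = 9 df with noncentrality 0.5/SE. The 95% CI half-width is about 2.262 × SE.

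| ρ | λ | F power | SE | 0.5/SE | Slope power (two-sided) | CI half-width |
|---|---|---|---|---|---|---|
| 0.5 | 3.13 | 23% | 0.283 | 1.77 | 35% | 0.64 SD |
| 0.7 | 5.21 | 36% | 0.219 | 2.28 | 53% | 0.50 SD |
| 0.8 | 7.81 | 53% | 0.179 | 2.80 | 70% | 0.40 SD |

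An equal fall gives the same λ and so the same F power. Simulation (20,000 replicates at ρ = 0.5 and 0.8) agrees: 23% and 53% for F, 36% and 70% for the slope.

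**Where the slope loses.** Take a 0.5-SD step after Day 1: means 0, 0.5, 0.5, 0.5, 0.5, with sum of squared deviations 0.4² + 4(0.1²) = 0.20. At n = 10, λ is 4.0 to 10.0 and F power is 28-65%. The fitted line shows a change of only 0.4 SD, so the slope has 24-51%. A rise on Day 5 only gives the same figures.

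**Other inputs (n = 10 unless stated; ρ 0.5-0.8 where a range is shown).**

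| Setting | F power | Slope power |
|---|---|---|
| Linear, ρ = 0.3 | 17% | 27% |
| Linear, ρ = 0.9 | 86% | 94% |
| Step from Day 3 | 42-84% | 47-85% |
| Linear, n = 12 | 27-63% | 42-80% |
| Linear, n = 8 | 18-42% | 28-58% |
| Linear, AR(1) errors, F uncorrected | 18-32% | 17-24% |
| Linear, AR(1) errors, F with Greenhouse-Geisser correction | 12-22% | 17-24% |

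Under AR(1) the uncorrected F also rejects 6-7% of the time when nothing changes.

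**Missing days.** A participant with four of five sessions stays in the analysis (SAP, Study Outcomes, 1.3), and missing data are excluded (SAP 5). A classical repeated measures ANOVA would drop that person, so fewer than 10 may contribute. A slope can be fitted to four days.

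**Undefined unit.** The Protocol takes eight readings per session: at rest, after Baseline, at minutes 10, 20, 30 and 40, after Post Training, and after overground training. SAP 2.1.2 does not say how these become one daily value. SAP 4.1.3.2 reports the maximum heart rate each participant reached, but not explicitly per day. The SD in these calculations is therefore a unit the plan has yet to define.

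**The case against.** A reader might infer that the SAP will declare the training tolerated if F is not significant. The documents do not say so. SAP 2.1.2 attaches no tolerance conclusion to the p value and reports group means (SD) as well, and levels of exertion, not only change, are part of tolerance. The nearest support is SAP 2.2.2, where absence of a significant difference between pre-tests is the condition for averaging them, but that concerns stance symmetry. Other signs of intolerance are also captured: severe fatigue that stops procedures is an adverse event, rest breaks are timed, and attendance is reported.

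A reader might also infer that any rise means identical work has become harder. That goes too far. Speed and tether force are constant, but visual feedback fades from 90% to 10%, rest breaks are optional, overground training runs 5 to 10 minutes, and participants are urged to load the weaker leg as much as they can. A rise could reflect more effort, so a two-sided analysis is appropriate.

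A third temptation is to replace the ANOVA. The step and last-day results argue against it, and a directed test would not cure low power: under the main assumptions the slope still misses 30-65% of linear rises. Low power is also expected in a pilot that claims none.

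All of this stands. If means are shown by day, they would also reveal the direction of a change. They would not say how precisely it is known, and that gap remains.

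**Conclusion.** The point holds as a low-cost improvement, not as an error that threatens the trial. SAP 2.1.2 tests change in exertion only through a test blind to order and direction, and it asks for no estimate or interval for that change. For a linear 0.5-SD rise at n = 10 and ρ of 0.5 to 0.8, a slope raises power by about 12 to 17 points (23% to 35%; 36% to 53%; 53% to 70%). That gain depends on the assumed shape and correlation: it disappears for step-like change and, against an uncorrected F, under AR(1) errors. The firmer benefit is a signed change with limits of about ±0.40 to ±0.64 SD under the main assumptions. That shows what a non-significant F leaves open, and it serves the planning of the larger trials that the SAP names as its purpose.

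**What to change.** In SAP 2.1.2:

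- Keep the group summaries, showing mean (SD) for each day, and keep the ANOVA.
- Define one daily value per session for RPE and for %HRmax.
- Add, for each measure, the within-participant linear slope over Days 1-5, using all available days, as SAP 2.2.2 already plans slopes over time for stance symmetry. Report it as the estimated Day 1 to Day 5 change with a two-sided 95% CI.
- State that change in exertion is interpreted from the direction and limits of that interval, and that non-significance is not evidence of no change.

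The cost is SAP wording and one extra analysis per measure, with no new data. The slope summarises step-like or single-day changes poorly; the retained day means and ANOVA cover those.
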